### **Maternal-fetal monitoring protocol**

[figure not shown]
[figure not shown]
Maternal-fetal monitoring will occur at the 24th, 28th, 32nd and 36th weeks of gestation. These periods reflect the most intensive developmental trajectories in fetal neurobehaviors, which become more complex as term advances, with a shift in the steepness of the developmental trajectory in most parameters between 28 and 32 weeks ([name], 2004). Quality continuous fetal heart rate monitoring is difficult prior to 24 weeks due to movement artifact. Monitoring sessions will last for 60 minutes and be conducted at 9 AM (the time of trough maternal B+N level) and again at 2 ½ hours after a single sublingual dose of B+N which corresponds to the time of peak maternal medication level. Women who are recruited for study participation will have their dose administered around 10 AM for 1 week prior to the time of fetal testing, and be on a stable dose of B+N during that time period. On the day of fetal testing, women will be instructed to eat breakfast 1 ½ hours prior to testing to control variation in blood glucose. Concurrent maternal-fetal monitoring will be digitized at 1000 Hz using an external analog to digital board using streaming software (Snapstream, HEM, Inc). The methodology and data processing techniques described have been used in our prior studies and are comprehensively described elsewhere ([name], 2015).

*Fetal data.* Fetal data will be generated from a Toitu (MT516) fetal actocardiograph, which detects fetal movement (FM) and fetal heart rate (FHR) through a single wide array transabdominal Doppler transducer and processes this signal through a series of filtering techniques. The actograph detects FM by preserving the remaining signal after band-passing frequency components of the Doppler signal that are associated

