*Maternal data.* Maternal physiologic signals will be amplified using a multi-channel, electrically isolated, bioamplifier. Electrocardiogram will be recorded from 3 carbon fiber disposable electrodes in triangulated placement; data will undergo R-wave detection, manual editing for artifact, and quantified as heart period (interval between R-waves in msec), heart period variability (standard deviation of successive heart periods), and an indicator of respiratory sinus arrhythmia which reflects vagal, predominantly parasympathetic influences on heart rate variation (Grossman & Kollai, 1993). Vagal tone will be indexed using the analytic technique developed by Porges (1986), which applies a 21-point polynomial to detrend sequential heart periods and a band-pass filter to extract the variance within the frequency band consistent with respiration within this age group (i.e., 24 to 1.04 Hz). Electrodermal activity (skin conductance) will be monitored from two electrodes with gelled skin contact area placed on the distal phalanxes of the index and middle fingers of the non-dominant hand affixed with adhesive. Skin conductance will be measured by administering a constant 0.5 volt root-mean-square 30 Hz AC excitation signal and detecting the current flow; scaling will be from 0 to 25 microsiemens. Respiratory data will be collected via a bellows gauge and quantified in terms of period (sec between breaths). Maternal data will be time synchronized and analyzed in conjunction with fetal data using the GESTATE program. Blood pressure will be measured at the start of each session using a sphygmomanometer. All maternal and fetal measures, with the exception of blood pressure, will be computed in 1-minute intervals and averaged over the 60 min recording.

Below are a schematic of the maternal-fetal monitoring system (left) and raw output values (right).

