*Infant variables.* Infant testing using the NNNS generates 13 summary scores (habituation, attention, handling, quality of movement, regulation, non-optimal reflexes, asymmetric reflexes, stress/abstinence, arousal, hypertonia, hypotonia, excitability and lethargy) that have been normatively described for both substance exposed and non-exposed infants (Tronick, 2004). Exploratory data analysis techniques will be used to determine distributions for each measure to determine how many of these will be used in the final analysis.

*Breastmilk variables:* Concentrations of B+N and major metabolites in breast milk, maternal and infant plasma

b. Statistical plan including sample size justification and interim data analysis.

*Fetal studies:* Individual analyses will be performed for three cardiac measures (FHR, FHR variability and accelerations) and two motor variables (overall activity, bout duration), and two synthetic measures (event and time series-based FM-FHR coupling, as described in the Procedures section. We will also evaluate effects of BN on maternal physiological function (heart period, respirations, cardiac vagal tone, skin conductance, and blood pressure).

Models for aims 1 and 2 will be longitudinal mixed effects linear regression models with random intercepts (Fitzmaurice, 2011). Additional models with fetal sex interactions will be fit to evaluate whether boys are differentially affected by either exposure, as we have observed in previous evaluating neurobehavior in methadone exposed infants (Jansson, 2010). Additionally, all analyses will be adjusted for maternal age, race, and non-opioid substance use.

For Hypothesis 1A, we will fit a model where the outcome for the  $i$ th individual at the  $j$ th timepoint ( $y_{ij}$ ) =  $\beta_0 + \beta_1 \text{peak} + \beta_2 \text{p}_2 - \text{p}_1 + \epsilon_{ij}$ , and  $\beta_1$  represents the difference, across timepoints, in the outcome between peak and trough measurements. For Hypothesis 1B, we will fit a similar model,  $y_{ij} = \beta_0 + \beta_1 \text{peak} + \beta_2 \text{time} +$

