## 8. Risks

a. Medical risks, listing all procedures, their major and minor risks and expected frequency.

There is a growing body of literature to support the relative safety and efficacy of buprenorphine use during pregnancy (Jones, 2010; Fischer, 2005; Jansson, 2010; Kakko, 2008, Lejeune, 2006), and the use of naltrexone, a compound similar to naloxone, produces no untoward effects when used in pregnancy in general to the mother or infant. One study evaluating fetal effects of maternal naloxone treatment at term found mild increases in fetal heart rate accelerations, fetal breathing and fetal movements (Arduini, 1986) all signs of fetal well-being. More recently, several observational studies have reported the relatively good outcomes in buprenorphine-naloxone exposed infants (Debelek, 2013, Dooley, 2016, Weigand, 2015, Gawronski, 2014) However, any medication used during pregnancy can present some risk to the mother and/or fetus. Risk to the neonate includes Neonatal Abstinence Syndrome (NAS), which occurs with less severity in buprenorphine, as compared to methadone exposed infants (Jones, 2010) however, there are no additional risks to the acquisition of NAS data. There are no known risks to fetal monitoring procedures for mothers or fetuses. There is no risk to the acquisition of breathalyzer testing, CO testing, or urine toxicology testing to subjects. Subjects will have additional urine toxicology screenings that CAP patients. There are no known risks of the NNNS exam that will be administered to infants.

For Buprenorphine-naloxone in particular, side effects are:

More Common reactions: Constipation (14% ), Nausea (23% ), Vomiting (11% ), Xerostomia (5% or greater), Dizziness (16% ), Headache (36% ), Somnolence (14% ) Withdrawal syndrome (25%), pain (22%), Diaphoresis (14%)

Less Common reactions: Vasodilatation (9%) Vomiting (8%)

Serious Reactions, but rare (<1%): Syncope, Application site reaction, Anaphylaxis, Hypersensitivity reaction, Loss of consciousness, Respiratory depression, Respiratory distress, Respiratory failure, Drug withdrawal.

Further, plasma and breast milk samples might induce minor bleeding, discomfort and bruising.

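### Maternal vagal tone: the filter band, read as .24 to 1.04 Hz, drops respiratory variation below 14.4 breaths/min, so vagal tone contrasts could partly reflect breathing rate

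*Combined protocol and SAP*

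**What the plan says.** In the Maternal-fetal monitoring protocol, under maternal data, the signal is the mother's: "Maternal physiologic signals will be amplified using a multi-channel, electrically isolated, bioamplifier". The vagal tone method "applies a 21-point polynomial to detrend sequential heart periods" and then band-passes the series to "extract the variance within the frequency band consistent with respiration within this age group (i.e., 24 to 1.04 Hz". Section 5 sets the age range at 18 to 44 years.

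Breathing is measured separately: "Respiratory data will be collected via a bellows gauge and quantified in terms of period (sec between breaths". Each testing day has a trough session at 9 AM and a second session, "again at 2 ½ hours after a single sublingual dose of B+N which corresponds to the time of peak maternal medication level". Measures are averaged over each 60-minute recording.

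Section 7a lists the RSA indicator among the maternal variables under the primary outcome heading. Section 7b plans to evaluate "effects of BN on maternal physiological function (heart period, respirations, cardiac vagal tone, skin conductance, and blood pressure". The stated adjustment covariates are maternal age, race and non-opioid substance use. Nothing in the documents uses respiratory period to choose or check the band, or to adjust vagal tone.

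**The concern.** The index is the heart-period variance that falls inside the band. It measures RSA only if the woman's breathing frequency lies inside the band too. When breathing falls below the lower edge, her RSA leaves the band and the index drops, even though vagal control has not changed.

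This matters because the planned comparisons are peak against trough and one opioid against another. If breathing rate differs between those conditions, the error follows the exposure and does not average out as noise. Using the same band in every group does not cancel it, because the loss depends on the breathing rate in each session. The adjustment set would not remove it. At stake is the interpretation of one maternal outcome, and of any use of it as a maternal marker under the exploratory hypothesis 3d.

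**Working it through.** **Inputs from the documents:** band limits 24 and 1.04 Hz as printed; adult women; peak and trough sessions. **Not in the documents, so assumed with a range:** mean resting breathing rate of 14 to 20/min; SD 3/min between women and 2/min within a woman; non-respiratory floor of 5 to 10% of RSA variance.

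**1. Convert the limits** (breaths/min = Hz x 60; period = 1/Hz).
- As printed: 24 x 60 = 1440/min, above the upper limit of 1.04 x 60 = 62.4/min, so it is not a pass band.
- Read as .24: .24 x 60 = 14.4/min, and 1/.24 = 4.17 s. The upper limit is 62.4/min, or 0.96 s.

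**2. Share of women averaging below the lower edge:** Phi((14.4 - m)/SD). For m = 16 and SD 3, Phi(-0.53) = 0.30. With SD from 2 to 4 the share is 54-58% at mean 14, 21-34% at 16, 4-18% at 18 and 0-8% at 20.

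**3. Spurious change with true RSA held constant.** For a woman with mean rate mu, the in-band share is p(mu) = Phi((62.4 - mu)/2) - Phi((14.4 - mu)/2). The index is ln(p + f), with f = 0.05 or 0.10. Averaging the change over mu ~ N(m, 3) when every woman slows by 1 or 2/min gives:

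| Mean rate m (/min) | Mean share of RSA variance in band | Change in ln index, 1/min slower | Change in ln index, 2/min slower |
|---|---|---|---|
| 14 | 46% | -0.26 to -0.32 | -0.52 to -0.65 |
| 16 | 67% | -0.21 to -0.24 | -0.45 to -0.53 |
| 18 | 84% | -0.12 to -0.14 | -0.29 to -0.33 |
| 20 | 94% | about -0.06 | -0.14 to -0.16 |

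At mean 16 the between-woman SD of the index in the same model is about 0.64 to 0.75, so a slowing of 1/min is worth about a third of an SD (0.24/0.75 = 0.32).

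**4. What another band would do.** For illustration only, 0.12 to 0.40 Hz (7.2 to 24/min) in the same model gives about 0.00 for 1/min and -0.02 for 2/min at mean 16. At mean 20 it gives a spurious rise of about 0.07 to 0.08 for 1/min, because its upper edge now cuts off fast breathers. Both limits therefore need to come from the women's data.

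**5. Cross-check with an explicit filter.** A constant-amplitude RSA signal was put through a 21-point cubic detrend and a .24 to 1.04 Hz band-pass. The documents do not give the polynomial order or the resampling interval, so a cubic and two intervals were assumed. At 500 ms the upper limit was capped just under 1 Hz. Share of variance kept:

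| Breaths/min | 500 ms | 250 ms |
|---|---|---|
| 20 | 0.74 | 0.92 |
| 16 | 0.70 | 0.18 |
| 14 | 0.25 | 0.04 |
| 12 | 0.01 | 0.005 |

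The direction agrees with step 3. The exact loss depends on filter details that the protocol leaves open.

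**The case against.** Several points on the other side stand.

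- The missing decimal point may come from the reading of the PDF. The inverted limits should not count against the plan, and .24 is an inferred value.
- A reader might infer that the band does not fit adult breathing at all. The documents do not support that: they give no breathing rate, and at an assumed mean of 16/min about 70% of women average above the lower edge and the band keeps 67% of RSA variance. The supportable statement is that the lower edge may cut off slower breathers.
- A reader might infer that slower breathing at peak will show as lost vagal tone. Slowing at peak is not documented. Section 8 names "Loss of consciousness, Respiratory depression, Respiratory distress, Respiratory failure" only among rare serious reactions (<1%), and women are to be on a stable dose for the week before testing. The documents do not contrast the drugs on breathing.
- The upper limit would need a heart rate of about 125 bpm (2 x 1.04 x 60 = 124.8) to be resolved from beat-to-beat data. That makes it an odd description of adult respiration, but it removes no RSA and adds nothing to the bias described here.
- Vagal tone is one ancillary measure. No confirmatory hypothesis names it, section 7b introduces it as an additional evaluation, and the predictors listed there for 3d do not include it. Power is based on fetal heart rate, NAS and NNNS.
- Respiratory period is recorded and is an outcome in its own right, so a shift in breathing would be visible to a careful reader. Stored ECG can be refiltered.

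The cited methods papers may explain the band, but they are not available here. Prior use would not in itself show that the band contains these women's breathing. Visibility of a breathing shift does not replace a planned check or adjustment.

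**Conclusion.** The point holds in a conditional form. On its only workable reading, the band discards RSA from breaths longer than 4.17 s in adult women, and the plan has no step that would detect or correct this in the vagal tone analysis. If some women breathe near or below 14/min, and breathing differs between peak and trough or between drugs, the vagal tone contrast could be partly an artefact of breathing rate.

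The unit conversion is exact. The size is not known: the spurious change per 1/min slowing varies about fivefold across assumed means of 14 to 20/min and is small at the upper end. It also rests on the assumed SDs, floor and filter shape. Fetal, NAS and NNNS outcomes and the sample size are untouched. This is a worthwhile correction to one maternal measure and does not threaten the study's main conclusions.

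**What to change.** In the maternal data paragraph of the Maternal-fetal monitoring protocol:

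1. Correct the printed band. Set both limits so that they contain the mothers' breathing frequencies seen in the bellows recordings, and state the basis. Use one fixed band for all groups and for both peak and trough, chosen without reference to group or session contrasts.
2. State the resampling interval and filter details, since the loss near the lower edge depends on them.

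In section 7b:

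3. Report respiratory period beside every vagal tone contrast, and add a supportive analysis that adjusts for it. This analysis should be supportive only, because breathing may itself be affected by the drug.

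Reprocess historical maternal ECG with the same band only if it is compared. The documents describe the historical comparison for fetuses and infants, and do not clearly plan a maternal one.

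The cost is a few protocol sentences and offline reprocessing of stored recordings, with no new data. The downside is that values will not be directly comparable with earlier publications that used the old band.

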## **Postnatal protocol**

**Neonates:** All neonates born to participants will be evaluated for signs and symptoms of neonatal abstinence syndrome (NAS) using a modified Finnegan Scale scoring system, previously described (Jansson, 2009c) to determine the severity of the infant's NAS display and the need for pharmacologic treatment. Scored items will be coded by symptom and severity of each symptom during the infant's hospitalization by nurses trained and experienced in administration. NAS parameters will be evaluated every 3-4 hours for a minimum of 4 days post-delivery and throughout the infant's hospitalization. Since NAS measurements are subjective, additional measures of NAS severity will include amount of medication (morphine sulfate, mg) used to treat NAS, the need or not for second medication to treat NAS, days of pharmacotherapy required, and length of hospital stay.

**Control and confounding measures:** All neonates at the hospital of record have a urine toxicology screen done at birth for benzodiazepines, opiates, THC, cocaine, methadone, barbiturates, phencyclidine, amphetamines and buprenorphine. All urine screens will be monitored and tracked for evidence of recent substance exposure. Infants will be excluded from further evaluation in the event of a significant medical complication which would include (but is not limited to): sepsis requiring antibiotic therapy, significant congenital malformation, birth at or transfer to another hospital, or preterm (<37 weeks) delivery.

**Neonatal health status.** Chart review will be used to extract salient data regarding labor, delivery, and neonatal parameters including infant sex, size, maturation, Apgar scores and any medical compromise and resuscitation methods employed. Maternal and infant toxicology results will be used to ascertain fetal exposures late in pregnancy. Additional infant medical history will be abstracted from infant medical records at the time of hospital discharge and will include all medications received and amounts, and any medical complications.

**Infants:** Infants will be evaluated through one month of age using a standardized neurobehavioral evaluation of high risk, especially substance exposed infants, the NICU Network Neurobehavioral Scale (NNNS; Lester, 2001). Evaluation of infant neurobehaviors can inform care providers (pediatricians, neonatologists, nurses, occupational / physical therapists, etc.) and parents regarding optimal care practices for this group. The NNNS is a comprehensive assessment of neurologic integrity and behavioral functioning, including withdrawal and signs of stress. Descriptive statistics for this scale have been provided from a prospective, large longitudinal study (Lester, 2002). The 13 NNNS summary scores (habituation, attention, handling, quality of movement, regulation, non-optimal reflexes, asymmetric reflexes, stress/abstinence, arousal, hypertonia, hypotonia, excitability and lethargy) have been normatively described for both substance exposed and non-exposed infants (Tronick, 2004). We have previously described the NNNS profile for methadone-exposed infants (Velez, 2009). Assessments will be performed by trained, certified investigators on days 3, 14 and 30 of life in the hospital or in a quiet lab adjacent to the infant's hospital room.

**Breastmilk: Maternal samples:** Subjects will provide plasma and breast milk at times of peak maternal medication levels (i.e. 2 – 2 ½ hours after maternal dose of B+N) on days 2, 3, 4, 14 and 30 post-partum.

**Infant samples:** Infant plasma will be obtained on day 14 coincident with a heel stick for routine pediatric care (i.e. PKU test) when feasible. NAS scores will be abstracted per the parent protocol.

**Analysis of breast milk and plasma samples:** Plasma and breast milk samples will be analyzed by Sam Houston State University in Huntsville, Texas. These investigators have extensive analytical experience with gas chromatography-mass spectrometry (GCMS) and liquid chromatography tandem mass spectrometry (LCMSMS) for many drugs of abuse, their metabolites and illicit pharmacotherapies. This plasma method investigates buprenorphine and norbuprenorphine concentrations as well as the glucuronide metabolites. New analytical methods will be developed for B+N and metabolites in breast milk based on the analysis of these analytes in multiple matrices.

b. Study duration and number of study visits required of research participants.

Study duration and the number of study visits depends on when during gestation (up to 34 weeks of gestational age) the participant enters the protocol. One hour long maternal-fetal monitoring sessions will occur up to 8 times, twice on 4 separate days at monthly intervals (i.e., 24, 28, 32 and 36 weeks). The number of monitoring visits depends on the gestational age at enrollment; participants enrolling after 24 weeks will have fewer visits. There are no study visits for neonatal testing, as all data are abstracted from neonatal charts as standard of care. Infants will be enrolled for 1 month after birth, and make 3 study visits (days 3, 14 and 30). For those participants enrolled in the lactation arm, study visits will occur on days 2,3,4,14 and 30 postpartum for sampling.

c. Blinding, including justification for blinding or not blinding the trial, if applicable.

This trial is not an open label trial; therefore, there is no blinding of study participants.

d. Justification of why participants will not receive routine care or will have current therapy stopped.

All CAP participants will receive standard substance use disorder, prenatal and pediatric care through the CAP program and in the newborn nursery or NICU. All participants from other treatment programs will receive care through their providers in those programs.

e. Justification for inclusion of a placebo or non-treatment group. NA

f. Definition of treatment failure or participant removal criteria.

There are several scenarios under which participants may terminate the study voluntarily or as a result of safety or compliance concerns. These include: patient choice (e.g., does not like buprenorphine-naloxone); voluntary or enforced discharge from the CAP or other treatment program (e.g., from incarceration, relocation, violation of CAP rules); physician choice (e.g., toxicity or side effects related to buprenorphine-naloxone); and ineligibility (e.g., violation of the study protocol, missing 5 consecutive days of buprenorphine-naloxone dosing, loss of pregnancy, development of fetal or maternal health condition).

Participants will be notified in the event that the research staff has determined that termination is necessary. Upon voluntary discontinuation or termination, participants will have the option of either being switched to methadone maintenance or continuing on B+N or buprenorphine provided there is a provider outside of CAP who will accept a B+N or buprenorphine transfer patient. It is expected that most participants who leave the study prematurely will request transfer to standard CAP methadone maintenance, as in previous protocols.

g. Description of what happens to participants receiving therapy when study ends or if a participant's participation in the study ends prematurely.

Women who are either voluntarily disenrolled from the protocol or whose study participation is terminated or completed will be transferred from buprenorphine-naloxone to buprenorphine or methadone maintenance. Transfer from buprenorphine to methadone is less complicated than transfer from methadone to buprenorphine. There is no risk of withdrawal precipitated by the first dose of methadone after buprenorphine. However, it may take several days for all buprenorphine to be eliminated from a participant's system. Clinical titration of methadone doses is essential to stabilize patients as quickly as possible. Commencement of methadone will begin not less than 24 hours after the last dose of buprenorphine.

